9.4 Other Efficacy Analyses

Change from baseline treatment comparison at each visit will be conducted using an MMRM model including treatment group, visit, treatment-by-visit interaction, and stratification factors as fixed effects, the baseline values associated with the endpoint as covariates. The REPEATED statement will be used for visit with blocks in the covariance matrix identified by subject nested within treatment group. The unstructured covariance structure will be used to estimate the within subject variance-covariance. If the model fails to converge, the first order autoregressive (AR[1]) covariance structure will be substituted. If the model still fails to converge, the compound symmetry (CS) covariance structure will be substituted. Denominator degrees of freedom will be computed using the Kenward-Roger method.

For binary efficacy endpoints, the frequency and percentage will be provided by treatment group unless otherwise noted.

9.4.1**Confirmed Improvement on the EDSS + and its components**

Confirmed 12-week disability improvement on the EDSS + or components of the EDSS + indicates a subject has clinically significant improvement at a visit as well as the next visit for one or more EDSS+ components, or if the next visit is missing, the subsequent visit. Confirmation may include assessments collected in the post-treatment follow-up period. The improvement confirmation must be in the same component of the EDSS +. If a subject has improvement in more than one component of the EDSS +, the subject must have confirmation in at least one of the same components to be considered as having confirmed disability improvement. For example, if a subject has clinically significant improvement in the T25FW at Week 12, the subject must have clinically significant improvement in the same component of the EDSS + at Week 24 (or if Week 24 is missing, Week 36) to be considered to have confirmed improvement.

Confirmed 24-week improvement on the EDSS + or components of the EDSS + indicates a subject has clinically significant improvement at 3 consecutive visits, or if one of the two subsequent visits are missing, subject demonstrates clinically significant improvement at two of the subsequent three visits. Improvement status after confirmed improvement is not considered, i.e., if a subject has disability improvement in one component of the EDSS + at Week 12 and Week 24, then this subject is considered to have 12-week confirmed disability improvement regardless of a Week 36 status of clinically significant worsening, no clinically significant change, or clinically significant improvement.

The 12-week and 24-week confirmed disability improvement response rate will be summarized for the study for the EDSS +, as well as each of the individual components for the mITT, RF, and MMIA analysis sets based on a non-responder imputation. The frequency and percentage will be provided by treatment group. The treatment comparison will be conducted using the logistic regression model adjusted for the stratification factors and baseline scores associated with the endpoint. The proportion of responders, difference in responder rate, and 95% confidence interval for the responder rate based on

Wald confidence limits will be presented based on the univariate summary. The odds ratio, and 95% confidence interval will be derived from the logistic regression model.

The analyses for confirmed disability improvement will be repeated for the RF and MMIA analysis sets as noted those respective sections.

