- If the Week 52 visit is missed, subject should be brought in as soon as possible and perform primary endpoint assessment (e.g., EDSS, 9HPT, or T25FW) for the Week 52 visit.
- If a Week 12, 24, or 36 visit is missed, subject should be brought in as soon as possible for an elezanumab infusion and perform primary endpoint assessments for the most recent missed visit.
- If a Week 16, 20, 28, 32, 40, 44, or 48 visit is missed, subject should be brought in as soon as possible for their missed infusion. Utilize the allowable visit windows to shift the subject into their predicted visit schedule. There must be a minimum of 14 days between infusions.

SCREENING:

	Informed consentEligibility criteriaMedical history	 Adverse event (AE) assessment Prior/concomitant therapy
SCALES – CLINICIAN- MEASURED	 Columbia-Suicide Severity Rating Scale (C-SSRS) 	 Expanded Disability Status Scale Plus (EDSS) Timed 25 Foot Walk (T25FW) 9-Hole Peg Test (9HPT)
T EXAMINATIONS	 12-lead electrocardiogram (ECG) Weight Height 	 Body mass index (BMI) Vital signs Physical examination Neurological examination
CENTRAL LABORATORY	Central laboratory tests	 Serum pregnancy test^a Urine drug and alcohol test
TIMAGING	 Brain and cervical spinal cord magnetic resonance imaging (MRI)^b 	

NOTES:

- a. Pregnancy tests are for females of childbearing potential. Results must be negative for study participation. Female subjects will perform monthly home urine pregnancy test during follow-up for 39 weeks (5 half-lives), after their last study drug dose.
- b. Baseline MRI must be performed before first dose. Non-scheduled MRIs after Baseline will be performed at the discretion of the subject's treating physician or in the case of early subject discontinuation, if it has been more than 4 weeks since the subject's most recent MRI. For MRI procedures, the visit window is ± 7 days.

RESCREEN

Subjects can be rescreened if they previously screen failed for the following reasons:

Discontinuation of an immunomodulatory less than 6 months before Screening

- Initiation of a new immunomodulatory or immunomodulatory dose change within 6 months of Screening
- Fall outside the 30-day screening period
- Experienced an MS relapse within 24 months before screening.
- Have a non-clinically significant laboratory abnormality that has now normalized.

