3.18 Dispense Study Drug

The unblinded pharmacist or qualified designee, under direct supervision of the unblinded pharmacist, will prepare study drug for IV administration. The unblinded pharmacist or qualified designee will dispense the blinded study solution to the clinic staff for IV administration to subjects beginning at the Week 0 – Baseline visit after all other Week 0 – Baseline procedures are completed.

Each site will be responsible for maintaining drug accountability records including product description, manufacturer, and lot numbers for all non-investigational products dispensed by the site.

Further information about study drug is in protocol Section 5.7.

COVID-19 Pandemic-Related Acceptable Protocol Modifications

In the event that study drug is not able to be administered due to study modifications related to the COVID-19 pandemic, bring the subject in as soon as possible for their missed infusion. Utilize the

allowable visit windows to shift the subject into their predicted visit schedule. There needs to be a minimum of 14 days between infusions.

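### Confirmed improvement is defined by consecutive visits with no minimum elapsed time, so a COVID-19 make-up assessment can yield a 12-week confirmed result from assessments 8 weeks apart, or about 2 at the extreme

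*SAP*

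**What the plan says.** SAP 9.4.1 defines 12-week confirmed disability improvement as the case where "a subject has clinically significant improvement at a visit as well as the next visit for one or more EDSS+ components", with the following visit used if the next one is missing. Its example works by visit name: improvement in a component at Week 12 must be seen again "at Week 24 (or if Week 24 is missing, Week 36) to be considered to have confirmed improvement". The 24-week version "indicates a subject has clinically significant improvement at 3 consecutive visits", with an allowance for one missing visit. No minimum number of days appears in either definition.

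Operations Manual 2.1, under the COVID-19 modifications, says that a subject who misses Week 12, 24 or 36 should return as soon as possible, be infused, and "perform primary endpoint assessments for the most recent missed visit". No latest date is given. For a missed Week 52, the "subject should be brought in as soon as possible and perform primary endpoint assessment", also without a latest date. The only spacing rule concerns infusions: "There must be a minimum of 14 days between infusions" (repeated in Operations Manual 3.18).

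SAP 4.3.1 mentions a visit window for the ORS but gives no day ranges. It does not say how a make-up assessment is assigned to a visit for confirmation.

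**The concern.** Confirmation is there to screen out transient change, and it does so only if enough time passes between the two assessments. The definition obtains its 12 or 24 weeks indirectly, by assuming that visits occur near their scheduled weeks. The make-up rule breaks that assumption: a late value carries the earlier visit's name, and the next scheduled assessment follows soon after. Values a few weeks apart tend to agree more often than values 12 weeks apart, so for those subjects the name of the endpoint would be wrong and confirmation easier to reach.

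Disruption was real. SAP 4.5 gives missed infusions and missed efficacy data as reasons for dropping the futility analysis, and SAP 5.1 creates the MMIA set because some subjects missed infusions. Confirmed improvement is compared between arms by logistic regression in three analysis sets (SAP 9.4.1) and again under multiple imputation (SAP 9.3.1).

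**Working it through.** **Inputs.** Efficacy assessments at Weeks 12, 24, 36 and 52 (Protocol Appendix D); a window of ±7 days on each visit and a last infusion at Week 48 (Protocol 4.1); the make-up rule and the 14-day infusion spacing (Operations Manual 2.1).

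**Step 1: the nominal interval reproduces.** 24 − 12 = 36 − 24 = 12 weeks = 84 days; 52 − 36 = 16 weeks = 112 days. If the first visit is 7 days late and the second 7 days early, the gaps are 84 − 14 = 70 days and 112 − 14 = 98 days.

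**Step 2: gaps with a make-up visit (next assessment on target).**

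| Missed visit | Made up at Week | Next assessment | Gap in weeks |
|---|---|---|---|
| 12 | 16 / 20 / 22 | 24 | 8 / 4 / 2 |
| 24 | 28 / 32 / 34 | 36 | 8 / 4 / 2 |
| 36 | 40 / 44 / 48 | 52 | 12 / 8 / 4 |

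Weeks 22 and 34 are the latest that the infusion spacing allows: (168 − 14)/7 = 22 and (252 − 14)/7 = 34. There is no infusion at Week 52, so that rule sets no floor for the last pair.

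**Step 3: 24-week triples.**
- Weeks 12/24/36: 168 days scheduled and at least 154 in window. With the first visit made up 14 days before the second, 14 + 84 = 98 days (14 weeks). With the second visit 7 days late and the third 7 days early, 98 − 14 = 84 days (12 weeks).
- Weeks 24/36/52: 196 days scheduled. The same steps give 14 + 112 = 126 days, and 126 − 14 = 112 days.

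**Step 4: effect on the 12-week rate (illustration).** The documents give no correlations, so these are assumptions: a latent normal score, 15% improved at each visit, and correlation 0.5^(gap in weeks/12). SAP 9.4.1 counts confirmation at any visit plus the next, so the rate is the probability that at least one of the pairs 12–24, 24–36 and 36–52 is improved at both visits.

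| Timing | Confirmed rate |
|---|---|
| On schedule | about 12.0% |
| Week 24 done at Week 28 | about 11.9% |
| Week 24 done at Week 32 | about 12.4% |
| Week 24 done at Week 34 | about 13% |
| Week 12 done at Week 22 | about 15.0% |

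These are simulated rates, reliable to about 0.1 point, for the 12-week endpoint only. The change is small for Week 24 because a late visit also lengthens the gap before it. Done at Week 34, it is 22 weeks after Week 12 (correlation 0.5^(22/12) = 0.28) and 2 weeks before Week 36 (0.5^(2/12) = 0.89). Week 12 has no earlier pair to lengthen, which is why it gives the largest rate of the cases run.

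The documents do not say how many subjects were affected. If 10% of an arm had the Week 22 case (assumed), its rate would be 0.9 × 12.0 + 0.1 × 15.0 = 12.3%, a shift of 0.3 points.

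**The case against.** **The 2-week gap is an extreme.** This stands. It needs a return about ten weeks late, although the Operations Manual asks for return as soon as possible. A return at Week 32 or 34 for Week 24 also implies consecutive missed infusions. On the natural reading that excludes the subject from the MMIA set, in which SAP 9.4.1 already repeats the analysis. The 8-week case is different: missing only the Week 24 infusion and returning at Week 28 is compatible with the MMIA set.

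**Analysis windows may exist elsewhere.** SAP 11.1 and 12.1 refer to a statistical programming plan, and date-based windows might assign a Week 34 assessment to Week 36. That could remove the 2-week case. Windows alone still would not guarantee 12 weeks: with cut-points midway between visits (assumed), Week 30 can count as Week 24 and Week 35 as Week 36, a 5-week gap.

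**A large inflation does not follow.** For a single pair of visits at 15% improvement, raising the correlation from 0.5 to 0.8 raises joint improvement from 5.8% to 9.1%. A reader might infer that the reported rate grows in that proportion. It does not: the endpoint combines three pairs, a late visit can lengthen one gap while shortening another, and only some subjects are affected.

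**Bias between arms does not follow either.** Make-up timing was driven by the pandemic in a randomised, double-blind trial, and nothing in the documents suggests that it differed by arm.

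**Conclusion.** The definition has a real but limited gap. As written, SAP 9.4.1 and Operations Manual 2.1 together allow a 12-week confirmed result from assessments 8, 4 or about 2 weeks apart, and a 24-week confirmed result spanning about 14 weeks, or 12 at the window extremes. The 8-week case needs only a return at the next 4-weekly visit.

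The likely effect on the 12-week rate is modest: about 12.0% on schedule against 11.9% to 15.0% among affected subjects, and less in a whole arm. That rests on the assumed 15% per visit, the assumed correlation and its decay, and make-up values keeping the missed visit's name. The main damage is to what the endpoint claims to measure. It is exploratory (SAP 4.3.3). The primary ORS and the secondary EDSS+ response at Week 52 need no confirmation and are unaffected.

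**What to change.** In SAP 9.4.1, define confirmation by actual assessment dates. The same component must be improved again at least 70 days after the first improvement (84 − 2 × 7) for 12-week confirmation, and at least 154 days after (168 − 2 × 7) for 24-week confirmation. It must also be improved at the assessments in between. Keep the existing missing-visit allowance, and state how a make-up assessment is assigned to a visit. For the multiple-imputation repeat (SAP 9.3.1), give imputed values their scheduled day.

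Both windows must be subtracted. Floors of 77 and 161 days subtract only one, and they would remove pairs and triples that comply with the protocol, as would a strict 84 days.

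The cost is a few sentences and some programming. No new data should be needed, since the baseline rule in SAP 9.1 already relies on dated assessments. The downside is that a few subjects with make-up visits lose confirmed status; one who is still improved at a later, sufficiently distant assessment keeps it. Protocol Appendix E reports that an efficacy analysis has already been done. If it included this endpoint, present the date-based version as a labelled supplementary analysis.

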The efficacy and safety analyses during the Treatment Period will be performed after the last subject completes the Week 52 visit. Except for certain pre-specified individuals, the sponsor and sites will remain blinded to group-level treatment efficacy and safety results until the last subject completes the Week 52 visit. Final safety analyses will be performed after the last subject completes the Follow-Up Period. Study sites and subjects will remain blinded for the duration of the study.

The schematic of the study is shown in Figure 1. Further details regarding study procedures are located in the Operations Manual (Appendix F).

See Section 5.1 for information regarding eligibility criteria.

Figure 1. Study Schematic

* During the Follow-up Period and after the Week 76 visit, female subjects of childbearing potential are to complete monthly home urine pregnancy tests for 39 weeks (5 half-lives) after last dose; and for all subjects AEs will be collected, whether solicited or spontaneously reported by the subject throughout the study and for a period of 39 weeks after the last dose of study drug. The Activity Schedule (Appendix D) includes subject visits through Week 76 only, but as mentioned above, female subjects of childbearing potential should report urine pregnancy results monthly up to 39 weeks after last dose.

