APPENDIX E. PROTOCOL SUMMARY OF CHANGES

Previous Protocol Versions

Protocol	Date
Version 1.0	30 August 2018
Version 2.0	01 February 2019
Version 3.0	07 August 2019
Version 4.0	25 November 2020

Protocol Summary of Changes

The purpose of this version is the removal of on-site assessments performed at Weeks 64 and 76 so that all visits in the Follow-up period can be conducted virtually. Other administrative revisions were made throughout the protocol, including the synopsis, and to the Operations Manual, to ensure consistency with the changes below:

- Protocol Section 4.1, Overall Study Design and Plan, Figure 1. Study Schematic and Protocol Appendix D. Activity Schedule: Remove Weeks 64 and 76 as an on-site visit.
- Update to Appendix F, Operations Manual: Section 2.1, Individual Treatment Period Visit Activities and Section 2.2, Individual Post-Treatment Period Visit Activities (Week 64 and Week 76) to remove vital signs, EDSS, T25FW, 9HPT, urine drug and alcohol test, PK and ADA sample collections; Section 3.6 Scales and Questionnaires table to remove EDSS T25FW, 9HPT from Follow-up at Weeks 64 and 76.

Rationale:

By January 2021, all study subjects had completed 52 weeks of therapy. A recent, planned efficacy analysis revealed that elezanumab therapy provided no beneficial effects. A lack of efficacy was observed on all endpoints.

The study initially had scheduled in person site visits at Week 64 and Week 76. The purpose of these visits was to perform assessment of the primary endpoint to better understand the durability of improvement observed at Week 52. Because there were no beneficial drug effects at Week 52, there is no scientific purpose to having the subjects return for in person visits. The ongoing COVID-19 pandemic also provides a strong justification for NOT having subjects perform unneeded in person site visits.

The collection of safety-related information by phone every 4 weeks through Week 76, including AEs, C-SSRS assessments, and pregnancy testing results will continue.

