During the course of the study, MRI scans will be performed at three time points: at Screening (Baseline MRI), Week 24 and Week 52/Early Discontinuation. The screening MRI will be evaluated by the local radiologist and the radiologist's report reviewed by the investigator before Dose 1 at Week 0-Baseline visit to determine subject's eligibility. For the subjects enrolled in the study, the Screening MRI will

serve as the Baseline MRI for assessment of MRI outcome measures. The time window for MRI is \pm 7 days. MRI scans from all protocol-required time points will be evaluated by a local radiologist, and the local radiologist's reports will be reviewed by the site investigator for disease activity. Sites should use the same local radiologist to evaluate all the MRI collected through the entire duration of the study to the extent possible.

The MRI scans will include all or a subset of the following parameters:

- 3D T1 weighted
- T2 FLAIR
- MTR
- PD/T2
- T1 post Gadolinium
- DTI
- Spine STIR

For each study site, the MRI scanner, associated equipment and imaging parameters may not be changed during the length of the study without prior sponsor approval.

COVID-19 Pandemic-Related Acceptable Protocol Modifications

MRI assessments may be collected up to 12 weeks after the projected visit for the missed time points at Weeks 24 and 52 with the sponsor's consent due to reasons related to the COVID-19 pandemic. However, all MRI assessments projected to be obtained on or before mid-November 2020 must be completed by the end of November 2020.

To accommodate scheduling of the vast volume of projected Week 52 MRIs in December 2020, at the discretion of the sponsor, sites may schedule Week 52 MRIs up to -28 days of their projected Week 52 visit.

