9.3.1 Sensitivity Analysis of the Primary and Secondary Endpoints

The primary and secondary endpoint analyses will be repeated for the RF and MMIA analysis sets as noted those respective sections.

Additionally, the analysis of ORS at Weeks 12, 24, 36, and 52, and the number and percentage of subjects with 12- and 24-week confirmed improvement for the EDSS+ and each of its components will be repeated based on multiple imputation (MI). First, a full dataset will be imputed using full data imputation MCMC. Data will be imputed for the

EDSS, T25FW, 9HPT-D and 9HPT-ND in a continuous fashion for each endpoint separately. Then, the definition of clinically significant improvement/no change/clinically significant worsening as seen in Section 4.3.1 will be applied to determine the components of the ORS or 12- or 24- week confirmed improvement status. The imputation model will include treatment group, type of MS, baseline use of immunomodulator therapies, baseline variable for the respective endpoint being imputed, and the non-missing post-baseline values for the variable that will be imputed (value at Week 12, 24, 36, 52, 64 and 76). The number of imputed datasets will be 30, and the random seed will be 123455. The ORS at each visit noted above will be summarized for each treatment group and compared to placebo using ANCOVA, with baseline values for each component of the EDSS + included in the model. The responder status with 12- and 24-week confirmed improvement will be analyzed with a logistic regression as noted in Section 9.4.1.

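### Does the exploratory confirmed-improvement endpoint need a stated data cut, given that Weeks 64 and 76 can supply the confirmation?

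*SAP*

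**What the plan says.** Confirmed improvement is an exploratory endpoint (SAP 4.3.3). Under SAP 9.4.1, 12-week confirmation requires improvement in the same component at a visit and the next one, or the one after if the next is missing. 24-week confirmation requires three consecutive improved visits, with an allowance for one missed visit. The section adds: "Confirmation may include assessments collected in the post-treatment follow-up period". Rates are summarized "for the mITT, RF, and MMIA analysis sets based on a non-responder imputation".

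SAP 9.3.1 repeats the confirmed analysis with multiple imputation (MI), and the imputation model uses the "value at Week 12, 24, 36, 52, 64 and 76".

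Neither section gives a data cut. On timing, Protocol 4.1 says: "The efficacy and safety analyses during the Treatment Period will be performed after the last subject completes the Week 52 visit". It names only safety analyses after follow-up. The rationale in Protocol Appendix E says "By January 2021, all study subjects had completed 52 weeks of therapy" and, of a planned efficacy analysis, "A lack of efficacy was observed on all endpoints".

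**The concern.** Confirmed improvement draws on both the Treatment Period and the follow-up period, and the plan assigns its analysis to neither time. If it is run at the last subject's Week 52, early enrollees have Weeks 64 and 76 and late enrollees do not. Non-responder imputation (NRI) then treats a visit that is not yet due like one that was missed.

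Late enrollment looks substantial: Operations Manual 3.17 has a provision "To accommodate scheduling of the vast volume of projected Week 52 MRIs in December 2020".

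Two things would be at stake. The absolute confirmed rates would depend partly on enrollment dates. And the MI repeat, meant to show sensitivity to missing data, would differ from the NRI result largely because it fills in visits that had not yet happened.

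**Working it through.** **The plan's own figure.** No design figure exists for this endpoint. The only one, about 80% power for ORS (SAP 4.4), reproduces: 55 × 0.9 = 49.5 per arm, and Φ(0.43 × √(49.5/2) − 1.282) = 0.80. Nothing below depends on it.

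**Which confirmations need follow-up.** Take improvements first seen at Weeks 12, 24, 36 or 52.
- 12-week: only Week 52 needs Week 64 (or Week 76 if Week 64 is missing), so 1 of 4.
- 24-week: Week 36 needs Weeks 52 and 64, and Week 52 needs Weeks 64 and 76, so 2 of 4.

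**Size for one component.** Assume improvement starts with probability 0.10 per visit and persists to the next with probability 0.70. Neither figure is in the documents. The chance of being improved is 0.10 × 0.7 + 0.90 × 0.10 = 0.16 at Week 24 and 0.16 × 0.7 + 0.84 × 0.10 = 0.196 at Week 36.
- 24-week, data to Week 52: 0.10 × 0.7² + 0.90 × 0.10 × 0.7² = 0.0931.
- Adding Week 64: + (1 − 0.16) × 0.049 = 0.1343.
- Adding Week 76: + (1 − 0.196) × 0.049 = 0.1737.
- 12-week, data to Week 52: 0.07 + 0.90 × 0.07 + 0.84 × 0.07 = 0.1918.
- Adding Week 64: + (0.804 − 0.07 × 0.3) × 0.07 = 0.2466. Week 76 adds nothing.

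With half the subjects lacking both visits, the rates are (17.4 + 9.3)/2 ≈ 13.3% and (24.7 + 19.2)/2 ≈ 21.9%.

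**Comparison between arms.** Control 0.10/0.70, active 0.15/0.80 (assumed):

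| Share with follow-up | 24-week odds ratio | 24-week difference (points) | 12-week odds ratio |
|---|---|---|---|
| None (Week 52 data only) | 2.10 | 8.5 | 1.91 |
| Half | 2.13 | 11.3 | 1.94 |
| All | 2.20 | 14.2 | 1.97 |

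The odds ratio hardly changes. The difference in responder rate, which SAP 9.4.1 also reports, does shift with the cut. A separate four-component simulation (8% versus 15% improved per component per visit, 10% dropout) agrees. From no follow-up to full follow-up, the odds ratio goes from 2.39 to 2.35 (24-week) and from 2.23 to 2.24 (12-week).

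**MI against NRI.** Take 10% dropout, spread evenly before Weeks 12, 24, 36 and 52, and let MI recover the rate with nothing missing. With half lacking follow-up, the 24-week gap is 5.2 points, against 1.6 if all had reached Week 76. So (5.2 − 1.6)/5.2 = 69% comes from visits not yet reached. For 12-week the gaps are 4.43 and 1.96, giving 56%.

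MI was also run on simulated four-component trials, using sequential normal regressions in place of the SAP's MCMC. The MI rate was stable, at 21–22% (24-week) and about 33% (12-week), wherever the model could be fitted. It could not be fitted in any of 60 trials when nobody had Week 64 or 76, and it failed in 10 of 60 when 25% and 10% had them.

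**How many would lack follow-up?** The documents do not say. If enrollment were even over A weeks and the cut fell on the last Week 52 visit, the shares reached would be 1 − 12/A (Week 64) and 1 − 24/A (Week 76). That is 54% and 8% for A = 26, and 82% and 63% for A = 65. A December 2020 cluster would lower these.

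**The date of the cut.** No date is given.
- At 31 January 2021, subjects whose Week 52 fell after 8 November 2020 (84 days earlier) lack Week 64.
- At 22 March 2021, the date of the current protocol, which calls the efficacy analysis recent, the limit moves to 28 December 2020. Nearly all of the December group then has a nominal Week 64, and the 12-week problem largely goes.
- The December group's nominal Week 76 runs from 18 May to 17 June 2021, so the 24-week effect remains at either date.

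**The case for a change.** The strongest case for a change is that the dependence on Weeks 64 and 76 is built into the definition and needs no assumed rates. Protocol 4.1 points to a Week 52 efficacy cut, and the remedy would be one sentence, a count by arm and a supplementary table restricted to Week 52. A later lock would not now give a common window either, because the current protocol replaced the on-site Week 64 and 76 assessments with telephone calls.

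Part of this stands. The cut is unstated, and at an early cut the absolute rates, the risk difference and the MI–NRI gap would partly reflect enrollment dates.

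The rest is weaker. The Protocol 4.1 sentence covers Treatment Period analyses, whereas this endpoint expressly uses later data. SAP 9.2 plans a summary of post-treatment ORS, so efficacy output from follow-up was foreseen, and Protocol 7.1 mentions an interim database lock, which suggests a later one. With the two follow-up visits in SAP 4.2.1, a lock after follow-up would have given every subject the same window. The removal of those visits followed the efficacy results and does not show that the SAP was deficient as written.

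The Week 52 table would also have lower power: about 51% against 60% (24-week) and 57% against 61% (12-week), at 55 per arm, one-sided 0.1, half lacking follow-up, under the assumed rates. Nor would it cure an imputation model with too few Week 64 and 76 values.

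**Conclusion.** No change to the plan follows. This is missing detail on an exploratory endpoint in a Phase 2a trial without multiplicity control, and an analyst cannot produce the table without settling it. The visit dates show who had reached Weeks 64 and 76, and a footnote can give the cut.

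Under the assumed rates, absolute 24-week rates can differ by about 8 points between full and no follow-up, and 12-week rates by about 5.5. The difference in responder rate moves too, from 8.5 to 14.2 points for 24-week confirmation, so these figures should be read with the cut in mind. The comparison with placebo stays unbiased because timing of enrollment is balanced by randomization in expectation, and the odds ratio is nearly constant. The primary ORS analysis and the main NRI analysis of unconfirmed Week 52 EDSS+ response use no Week 64 or 76 data.

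The sizes rest on assumed onset, persistence, dropout pattern and share lacking follow-up. The direction and the absence of bias between arms do not. The one practical caution is that the 9.3.1 imputation may not be estimable if very few subjects have Week 64 or 76 values at the cut. That would show when the model is run.
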